12.3 Determination of sample size

The sample size for this study was selected to be consistent with the research hypothesis as described in Section 1.2.

The primary variable of this study is the time from randomisation to occurrence of peptic ulcer. The result of a phase III study (D961FC00003) was used to estimate the occurrence rates of peptic ulcer at 6 months for D20 and placebo. The event rates for peptic ulcer at 6 months were 1.5% for D20 and 7.4% for placebo, respectively.

In order to detect a difference in time to occurrence of peptic ulcer between D20 and placebo with two-sided 2.94% significance level and >90% power, assuming a recruitment period of 12 months and a minimum follow-up of 6 months; i.e. the total length of study is estimated to be 18 months, at least 36 events will be required. To get the number of events during the period in total 426 subjects (213 subjects per group) will be randomised in the study taking 15% of subjects who may discontinue the study without an event into consideration.

The final analysis of the primary variable will be performed when 36 events are observed. The nominal 2-sided significance level for all analyses will be 5%, except for the primary variable, where the nominal significance level will be adjusted using the Pocock-like alphaspending function with Lan-DeMets approach to allow for a single interim analysis.

In this study, at least 100 subjects who are randomised to D20 will continue taking investigational product for one year to obtain long-term safety data because one-year safety data from at least 100 subjects are required according to the ICH E1 guideline "The Extent of Population Exposure to Assess Clinical Safety for Drugs Intended for Long-Term Treatment of Non-Life-Threatening Conditions".

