9.5 Study timetable and end of study

The end of the study is defined as 'the last visit of the last subject undergoing the study'.

The study may be terminated at individual centres if the study procedures are not being performed according to GCP, or if recruitment is slow. AstraZeneca may also terminate the entire study prematurely if concerns for safety arise within this study or in any other study with D961H or OPZ.

Planned duration of the study:

Study period: January 2010 (First subject in) to July 2011 (Last subject last visit)

Registration period: January 2010 (First subject in) to January 2011 (Last subject in)

Registration period is changed depending on accumulation speed of gastric and/or duodenal ulcer events.

The principal investigator will be notified when the subject randomisation has completed and required number of gastric and/or duodenal ulcer events are confirmed.

Discontinuation or suspension of the whole study programme

If AstraZeneca decides to prematurely terminate or suspend the study, the Principal Investigator, sub-investigator, the head of the institution (for Japan), and regulatory authorities should receive written notification of the reasons for the premature termination or suspension.

The Principal Investigator/sub-investigator will immediately notify the decision to the subjects, give appropriate medical treatment; take necessary measures, and record treatment or measures provided on the source documents.

Completion of the study (for Japan)

Upon terminating the study, the Principal Investigator/sub-investigator will report in writing the completion of the study as well as the summary of the results to the head of the study site in accordance with the institution's rules. The head of the study site, who is informed of the termination by the investigator, will provide a written notification of the results to the IRB and AstraZeneca.

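### Section 12.3's 426 subjects yield 36 events in 18 months only on a no-dropout calculation, so the stated 15% discontinuation allowance is not in the figure

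*Protocol*

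**What the plan says.** Section 12.3 of the protocol builds the design in four steps.

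- Rates: "The event rates for peptic ulcer at 6 months were 1.5% for D20 and 7.4% for placebo, respectively".
- Events: a log-rank comparison "with two-sided 2.94% significance level and >90% power", for which "at least 36 events will be required".
- Calendar: "assuming a recruitment period of 12 months and a minimum follow-up of 6 months", so 18 months in total.
- Subjects: 426, split equally as 213 per arm, to obtain those events in that period. The section says this number was reached "taking 15% of subjects who may discontinue the study without an event into consideration".

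The same section makes the analysis event-driven: "The final analysis of the primary variable will be performed when 36 events are observed". Section 9.5 gives a matching calendar, with first subject in January 2010 and last visit in July 2011. It adds that the registration period may change with the speed at which ulcer events accumulate. Section 12.2.3 places one interim analysis at 18 events, half of 36, and that is the basis of the 2.94% level.

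**The concern.** A sample size that includes a 15% allowance for loss should be clearly larger than the size needed without loss. Here the two are almost equal. If the allowance is missing, 426 subjects should not be expected to produce 36 events by month 18, and the July 2011 date rests on nobody leaving early. The trigger of 36 fixes the data cut-off, the final analysis and the information fraction at the interim, so its timing and its stated basis should be right.

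A second, smaller point concerns the event count. At the stated rates the usual formulas reach 90% power with fewer than 36 events, so the text does not show why 36 is the required number.

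**Working it through.** **Inputs** (all from Section 12.3): 6-month event rates 7.4% (placebo) and 1.5% (D20); two-sided alpha 0.0294; uniform recruitment over 12 months; follow-up of 6 to 18 months; 213 per group; 15% discontinuing without an event. Constant hazards, uniform recruitment and the timing of dropout are my assumptions; the section does not state them.

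**Hazards.** λ = −ln(1 − p)/6 per month: placebo 0.01281, D20 0.00252. HR = ln(0.985)/ln(0.926) = 0.197.

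**Reproducing 426.** The mean event probability over 6 to 18 months of follow-up is 1 − [exp(−6λ) − exp(−18λ)]/(12λ).
- Placebo 0.1417, D20 0.0297, sum 0.1714.
- Expected events with no dropout: 213 × 0.1714 = 36.5. Stopping follow-up at the 72-week maximum gives 36.3.
- Subjects needed for 36 events with no dropout: 2 × 36/0.1714 = 420.

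So 426 matches the no-dropout calculation with about 1.4% to spare (426/420).

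**Adding the 15%.** With a constant dropout hazard η, the event probability becomes λ/(λ+η) × {1 − [exp(−6(λ+η)) − exp(−18(λ+η))]/(12(λ+η))}. The cases differ in how fast the 15% is lost.

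| Loss pattern | Expected events, month 18 | N for 36 events by month 18 | Month of 36th expected event (without / with 72-week cap) |
|---|---|---|---|
| None | 36.5 | 420 | 17.8 / 17.9 |
| 15% by month 18, η = −ln(0.85)/18 = 0.0090 | 34.5 | 444 | 18.6 / 18.8 |
| 15% by month 12, η = 0.0135 | 33.6 | 457 | 19.0 / 19.3 |
| 15% contribute nothing, 0.85 × 36.5 | 31.0 | 494 | 20.1 / 20.8 |
| 15% by month 6, η = 0.0271 | 31.0 | 495 | 20.5 / 21.4 |

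If instead 15% of all subjects are seen to discontinue at a constant rate, the count is 33.4 and the N is 459. The last row is the harsh end, because that rate, if it continues, loses well over 15% in total. No pattern tried returns 426.

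**Event count.** With z-values 2.178 and 1.282, (2.178 + 1.282)² = 11.97.
- Schoenfeld: 4 × 11.97/(ln 0.197)² = 4 × 11.97/1.627² = 18.1, so 19 events.
- Freedman: 11.97 × (1.197/0.803)² = 26.6, so 27 events.
- Log-rank simulation: power 0.90 at 22 events, 0.95 at 27 and 0.99 at 36.
- Power at 36 events: Schoenfeld Φ(3 × 1.627 − 2.178) = 99.7%; Freedman Φ(6 × 0.803/1.197 − 2.178) = 96.8%.
- HR at which 36 events is the 90% requirement: 0.27 (Freedman) to 0.32 (Schoenfeld).

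**Sensitivity.** Table 1 of the protocol gives 1.1% for D20 in the same source study. With that rate, 426 subjects give 34.8 expected events without dropout and 29.6 to 32.9 with 15% loss.

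**The case against.** The strongest reply is that very little turns on this. The final analysis waits for 36 events, so power does not depend on the date. Section 9.5 lets registration follow event accumulation, and 18 months is described as an estimate. Discontinuers are censored at their last EGD and are asked to have the final-visit tests, so they do contribute follow-up. The mild end of the range is then the more natural one, with a shortfall of about 1.5 to 2 events against a Poisson standard deviation of about 6. With the 72-week cap, the chance of at least 36 events by month 18 falls only from about 54% to about 41%. All of that stands, and it limits the size of the point. It does not put the 15% into the 426: the section says the allowance was made, and its inputs show that it was not.

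On the event count, a reader might infer that 36 is an error, that the power claim is false, or that 36 is an accidental doubling of 18.1. The documents support none of these. The claim is for power above 90%, and 36 events give about 97% to 99.7%. A margin is also reasonable, because the rates come from an overseas study while this trial enrols Asian patients with prior ulcer, all taking gefarnate. Nothing in the text indicates a doubling. Nor can it be said that placebo subjects are held longer than the power claim needs: that reading treats the claim as exactly 90%, and the 18-event interim already allows an early stop for superiority.

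**Conclusion.** The statement about dropout is wrong as written. Under constant hazards and uniform recruitment, 426 is the no-dropout number. With 15% loss the expected count at month 18 is 31.0 to 34.5, and 36 events by then would need about 444 to 494 subjects. At 426 subjects the 36th event is expected at about month 19, or month 20 to 21 with early loss: a delay of roughly 0.6 to 3.4 months against the stated 18. The size depends on dropout timing, which the protocol does not give.

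A reader might infer that the trial is underpowered. It is not, because the trigger is the event count; the cost is calendar time or added recruitment.

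On the event count, the only fault is the wording that 36 is required. At the stated rates 19 to 27 events give 90% power, so either the true power or the hazard ratio behind 36 is undisclosed. That is conservative and needs clarification only.

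**What to change.** Keep 426 subjects, the 36-event trigger and the 18-event interim. In Section 12.3:

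1. State that 36 events give about 97% to 99% power at the assumed rates, or give the hazard ratio (about 0.27 to 0.32, by formula) for which 36 events is the 90% requirement.
2. Either remove the claim that 15% discontinuation is included and say that 18 months assumes no loss, or state the assumed dropout timing with the resulting 31 to 34.5 expected events at month 18.
3. Correct the 18-month duration there, and July 2011 in the synopsis and Section 9.5, to match. Month 18 is July 2011, so month 19 is about August and month 21 about October 2011.

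Do not lower the trigger to fit 90% power. With 27 events, an 18-event interim would sit at 18/27 = 67% information, and the 50% basis of the 2.94% level would be lost.

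The cost is one rewritten paragraph, the timetable entries and a slightly longer stated calendar. No subjects are added, and the error rate and analysis plan are unchanged.

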12.4 Central evaluation committee and independent data monitoring committee

12.4.1 Central evaluation committee

A central evaluation committee consisting of gastrointestinal specialists will be appointed for this study to validate the diagnosis by the investigator based on the EGD findings.

The central evaluation committee will review EGD findings regarded as ulcer scar, past EGD findings used for diagnosis in case of unclear scar, and EGD findings on the bases of which the investigator made a diagnosis of gastric or duodenal ulcer after starting the study treatment, as appropriate, for all subjects randomized to the investigational product. The central evaluation committee will report the review results to the sponsor.

The timing of meetings and responsibilities of the central evaluation committee will be specified separately.

12.4.2 Independent Data Monitoring Committee

An Independent Data Monitoring Committee (IDMC) will be appointed for this study. IDMC perform the interim analysis and decide on a recommendation on continuing or discontinuing the study. (See Section 12.2.3)

The timing of meetings and responsibilities of the IDMC will be specified separately.

13. IMPORTANT MEDICAL PROCEDURES TO BE FOLLOWED BY THE INVESTIGATOR

13.1 Medical emergencies and AstraZeneca contacts

The Principal Investigator is responsible for ensuring that procedures and expertise are available to handle medical emergencies during the study. A medical emergency usually constitutes an SAE and is to be reported as such, see Section 6.4.4

In the case of a medical emergency the investigator may contact the Study Delivery Team Leader. If the Study Delivery Team Leader is not available, contact the Study Delivery Team Physician at the AstraZeneca Research and Development.

Name	Role in the study	Address & telephone number

13.2 Overdose

In this study, intake of 6 or more capsules of the investigational product per day by a subject will be considered an overdose.

No information is available on known antidotes for the investigational product. In case of an overdose or a suspected overdose, appropriate supportive measures should be given and the subject should be observed for vital condition.

In an overdose occurs, the following actions should b taken:

- An overdose with associated AEs is recorded as the AE diagnosis/symptoms on the relevant AE modules in the eCRF and on the Overdose eCRF module.
- An overdose without associated symptoms is only reported on the Overdose eCRF module.

If an overdose on an AstraZeneca study drug occurs in the course of the study, then investigators or other site personnel inform appropriate AstraZeneca representatives **within one day**, ie, immediately but no later than **the end of the next business day** of when he or she becomes aware of it. The designated AstraZeneca representative works with the investigator to ensure that all relevant information is provided to the AstraZeneca Patient Safety data entry site.

For overdoses associated with SAE, standard reporting timelines apply, see Section 6.4.4. For other overdoses, reporting should be done within 30 days.

13.3 Pregnancy

All outcomes of pregnancy should be reported to AstraZeneca.

13.3.1 Maternal exposure

If a subject becomes pregnant during the course of the study investigational product should be discontinued immediately.

Pregnancy itself is not regarded as an adverse event unless there is a suspicion that the investigational product under study may have interfered with the effectiveness of a contraceptive medication. Congenital abnormalities/birth defects and spontaneous miscarriages should be reported and handled as SAEs. Elective abortions without complications should not be handled as AEs. The outcome of all pregnancies (spontaneous miscarriage, elective termination, ectopic pregnancy, normal birth or congenital abnormality) should be followed up and documented even if the subject was discontinued from the study. The PREGREP module in the eCRF is used to report the pregnancy and the PREGOUT is used to report the outcome of the pregnancy.

If any pregnancy occurs in the course of the study, then investigators or other site personnel inform appropriate AstraZeneca representatives **within one day** ie, immediately but no later than the **end of the next business day** of when he or she becomes aware of it.

The designated AstraZeneca representative works with the investigator to ensure that all relevant information is provided to the AstraZeneca Patient Safety data entry site within 1 or 5 days for SAEs, see Section 6.4.4 and within 30 days for all other pregnancies.

The same timelines apply when outcome information is available.

